## **Follow-up**

All extremely preterm infants hospitalized in our unit are discharged home at about GA 35+0. Infants regionally belonging to another hospital are usually transferred to the “home hospital unit” not earlier than GA 28+0. After hospital discharge, all extremely preterm infants are routinely followed-up according to a nationwide schedule, until the age of 5,5 years. Data mostly concerning children’s growth as well as neurological and psychomotor development are collected, and interventions are made as needed.

Study participants will be followed-up until full term corrected age (GA 40 +0), and medical information including possible treatments as well as diagnosis of NEC or other gastrointestinal complication, sepsis, PDA, BPD, ROP, IVH, hyperbilirubinemia, growth parameters (weight, length, head circumference) and mortality will be collected by the investigators from the treating physicians and electronic medical records. All the clinical, laboratory and radiological findings of infants treated at our unit are routinely and continuously registered in detail, with the use of medical computer software, during the whole hospitalization period, and these data will be readily accessible to the investigators. Besides, data on children’s growth and neurological development will be collected from the electronic medical records, until the age of 5,5 years. The above-mentioned data of study participants that have been transferred to the home or other hospital unit will be collected by the investigators though communication with the treating physician at the respective hospital.

## **Documentation**

All data relevant to the study collected by the investigators will be registered and de-identified in electronic database with password-protected access allowed only to the investigators.

### **Refuse to enrollment and subject dropouts**

Refusals to enroll the study and dropouts of the study and the respective reasons will be documented and reported in the results. Effort will be made to replace each of these subjects with another infant of the same gestational age.

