## **Allocation**

A blinded research coordinator will randomly assign eligible infants using a computer software-based randomization system (default) or sealed, numbered, and opaque envelopes (back-up), with a 1:1 allocation ratio, as soon as possible and not later than 24 hours from birth.

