## **Eligibility criteria**

All infants born extremely preterm in GA between 22+0 and 26+6 weeks at the NICU of University Children's Hospital in Uppsala will be consecutively recruited in the study during the years 2018 – 2022. Written informed consent will be obtained from both parents before enrollment in the study.

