### **Intervention**

The following intervention will be applied to the intervention group: specially trained pediatric surgeon will administer 10ml/kg pre-warmed (37°C) normal saline via a single-use rectal tube of size 6FR twice per day, aiming at a depth of maximum 10 cm/kg, starting after randomization and not later than 24 hours of age, and continued until full enteral nutrition of 170ml/kg/day is achieved or NEC diagnosis (Bell stage II or more) is established, whichever comes first. However, the intervention will be applied at a maximum of 2 weeks from birth. Besides, the intervention will be withheld in case of suspicion of infection or NEC but will be resumed if antibiotics are not introduced and discontinuation of feeds does not exceed 48 hours. Early stopping criteria include infection / sepsis or NEC suspicion necessitating prolonged discontinuation of feeds > 48 hours and / or antibiotics, circulatory instability or adverse events. The intervention will only be applied at the NICU of University Children's Hospital in Uppsala and will be discontinued if the infant is transferred to another hospital. Standard departmental guidelines will be followed regarding ventilation, choice of PN, invasive monitoring, and management of sepsis and/or necrotizing enterocolitis (NEC) for both the intervention and the control groups.

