### **Completion of the study**

The study will be completed when the number of 100 subjects per study arm is reached (a maximum of 130 subjects per study arm will be allowed), estimated to be achieved by the year 2022 (and not later than year 2023).

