### **Statistical analysis**

Numerical data with a gaussian distribution will be expressed as means (standard deviation), otherwise as medians (ranges). We will use the Anderson-Darling test to assess the normality of the data. Numerical values will be compared between intervention and control groups using t-tests or the Mann-Whitney U test. Categorical variables will be compared using  $\chi^2$  or Fisher's exact tests. Times to achieve full enteral feeding will be compared by the log rank test. Multiple Cox regression analysis will be used to adjust for covariates, such as gestational age and birth weight. IBM SPSS software (current version at the time of publication) will be used for all calculations and a p-value of <0,05 will be considered significant.

Interim analysis will be conducted when 35 infants have been recruited in each study arm (estimated about 1,5 years from study start). Another interim analysis will be conducted when 65 infants have been recruited in each study arm (estimated about 3 years from study start). Unplanned interim analysis will also be conducted in case of subjectively estimated too obvious difference between the groups regarding the primary outcomes, at any time during the study. The study will be discontinued as soon as an interim analysis shows statistically significant results regarding the primary outcomes or severe adverse events.

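### Randomised dropouts are to be replaced, and nothing in the plan keeps them in the count or analysis of their allocated arm

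*Combined protocol and SAP*

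**What the plan says.** The section on refusals and dropouts treats the two groups together. It promises that refusals and "dropouts of the study and the respective reasons will be documented and reported in the results", and then adds: "Effort will be made to replace each of these subjects with another infant of the same gestational age". Dropout is not defined.

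The other relevant sections are:

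- **Completion of the study:** "The study will be completed when the number of 100 subjects per study arm is reached", with a ceiling of 130 per arm. It does not say whether a replaced infant still counts or what the extra 30 are for.
- **Statistical analysis:** the first look is set by recruitment ("Interim analysis will be conducted when 35 infants have been recruited in each study arm"). The section names tests for comparing the two groups but gives no analysis population and no rule for withdrawn infants.
- **Eligibility criteria and Allocation:** eligible infants "will be consecutively recruited in the study" and are randomised "with a 1:1 allocation ratio, as soon as possible and not later than 24 hours from birth". No separate route is described for replacements.
- **Intervention and Follow-up:** lavage "will be discontinued if the infant is transferred to another hospital", yet "data of study participants that have been transferred to the home or other hospital unit will be collected by the investigators". This suggests that transfer, or stopping lavage, is not dropout, but neither section says so outright.
- **Ethical considerations:** parents may leave the study at any time, so withdrawal after randomisation is foreseen.

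**The concern.** Replacing a family that declines before randomisation does no harm. Replacing an infant who has already been randomised is different. If the replacement takes that infant's place in the count and in the analysis, the arms are no longer the groups that randomisation formed. Matching the replacement on gestational age does not correct for selection on clinical course.

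The trial is unmasked, and only the intervention arm has a scheduled twice-daily procedure. Withdrawal by parents could therefore differ between arms and be related to how the infant is doing. If those infants were replaced and left out, NEC could differ between arms with no true effect. Time to full enteral feeding could be affected in the same way. It is not quantified here because the documents give no distribution of it for this unit.

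**Working it through.** **The plan's own figure.** The sample size section gives about 100 per arm for NEC 15% v 8%, power of at least 70%, 5% level. The two-sided pooled formula, with mean rate 0.115, gives n = [1.96·√(2·0.115·0.885) + 0.524·√(0.15·0.85 + 0.08·0.92)]² / 0.07² ≈ 256 per arm (195 one-sided), so 100 is not reproduced. That is a separate matter. The check below uses 100 per arm because that is the stated target.

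**Inputs from the protocol.** NEC 15%; planned difference 15 − 8 = 7 points; 100 per arm; p < 0.05; chi-square or Fisher's exact test for categorical data.

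**Assumptions.** No true effect; all dropouts' outcomes lost; 100 completers per arm analysed; uncorrected two-sided chi-square; a single final analysis. Dropout fraction d and relative NEC risk RR of dropouts against the whole arm are varied, because the documents give neither.

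**Step 1: NEC rate among completers.** Rate = (0.15 − d·0.15·RR)/(1 − d). For d = 0.10 and RR = 2, this is (0.15 − 0.03)/0.90 = 0.1333.

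**Step 2: rejection probability.** Exact enumeration of the two binomials, n = 100 each.

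| Dropout pattern | Lavage v control NEC | False difference in favour of lavage (points) | Type I error | False benefit of lavage |
|---|---|---|---|---|
| None, or average risk (RR 1) | 0.1500 v 0.1500 | 0 | 5.09% | 2.55% |
| Lavage arm 5%, RR 1.5 | 0.1461 v 0.1500 | 0.39 | 5.16% | 3.05% |
| Lavage arm 10%, RR 0.5 | 0.1583 v 0.1500 | −0.83 | 5.41% | 1.73% |
| Lavage 10%, control 5%, RR 2 | 0.1333 v 0.1421 | 0.88 | 5.46% | 3.80% |
| Lavage arm 10%, RR 2 | 0.1333 v 0.1500 | 1.67 | 6.40% | 5.29% |
| Lavage arm 10%, RR 3 | 0.1167 v 0.1500 | 3.33 | 10.73% | 10.31% |
| Lavage arm 20%, RR 2 | 0.1125 v 0.1500 | 3.75 | 12.37% | 12.06% |

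The last three rows are upper-end illustrations.

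**Step 3: what keeping dropouts in the analysis recovers.** Suppose only half of the dropouts' NEC events can be used, the rest count as no NEC, and all 100 randomised per arm stay in the denominator. The lavage rate is then 0.15 − 0.5·d·0.15·RR = 0.1350, 0.1275 and 0.1200 for the last three rows. Type I error is 6.1%, 7.5% and 9.6%.

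**Step 4: numbers to randomise if 100 must have outcome data.** 100/0.90 = 111.1, so 112 per arm at 10% loss; 100/0.80 = 125 at 20%. Both lie under the ceiling of 130.

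**Step 5: dilution.** If a fraction d of the lavage arm gets no benefit, its NEC rate is 0.08(1 − d) + 0.15d. That is 0.087 at 10% and 0.094 at 20%, so the planned 7 points becomes 6.3 or 5.6.

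**The case against.** The strongest reply is that bias needs both replacement and exclusion, and only replacement is written. Replacement could simply mean recruiting extra infants up to the ceiling of 130, with dropouts still analysed. That reading is open, but so is the other one, and nothing in the protocol chooses between them. In an unmasked trial the choice should be made before outcomes are known.

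The second reply concerns size. Outcomes come from routine records, so NEC diagnosed before withdrawal is already documented. Lavage lasts at most two weeks from birth, which leaves parents who object to it only a short window to withdraw. The upper-end cases also demand a lot: 20% dropout at twice the risk means that 0.20 × 2 = 40% of the lavage arm's NEC occurs in infants who left, and 10% at three times means 30%. No figure in the protocol supports either. This stands: the large numbers are illustrations, and the mild patterns barely move the error rate.

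Third, Fisher's exact test is also allowed and is more conservative. Its baseline is 3.3%, and the three upper-end cases give 4.2%, 7.5% and 8.8%. The levels are lower, but the bias runs the same way.

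Finally, the parental consent form was not available and may already settle the use of data after withdrawal. That limits what the fix can recover, but it does not settle who is analysed.

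**Conclusion.** The point holds. The replacement rule reaches randomised infants, and nothing keeps them in the count or analysis of their allocated arm. Reporting dropouts and their reasons, as the protocol requires, does not put them in the comparison.

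The consequence is conditional. There is no bias if dropout is unrelated to outcome, or equal in both arms at the same risk. The bias becomes material only with dropout concentrated in one arm at clearly raised risk. In the worst case shown, the false NEC difference is 3.75 points, just over half the planned 7. All of this assumes that dropouts' outcomes are lost, which the protocol neither states nor excludes. The change should be made because it is cheap, not because large bias is shown to be likely.

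**What to change.** 1. Limit replacement to refusals before randomisation.
2. Define dropout as withdrawal from the study, and say that stopping or withholding lavage, or transfer, is not dropout.
3. Analyse every randomised infant in the allocated arm, using records to GA 40+0 as far as consent allows and keeping events recorded before withdrawal. A completer analysis may be secondary.
4. State that the 100 per arm counts randomised infants. If infants with outcome data are to be counted instead, say that extra infants, up to 130 per arm, enter only through the ordinary 1:1 randomisation and are added to the dropouts, not substituted for them.

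The cost is mainly wording, since outcomes are already collected from routine records, including after transfer. The consent form must be checked for use of data after withdrawal, and the gain depends on it, as the half-recovery figures show. The downside is some dilution of the effect estimate, from 7 points to 6.3 or 5.6 in the cases worked above.

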### **Completion of the study**

The study will be completed when the number of 100 subjects per study arm is reached (a maximum of 130 subjects per study arm will be allowed), estimated to be achieved by the year 2022 (and not later than year 2023).

### **Statistical analysis**

Numerical data with a gaussian distribution will be expressed as means (standard deviation), otherwise as medians (ranges). We will use the Anderson-Darling test to assess the normality of the data. Numerical values will be compared between intervention and control groups using t-tests or the Mann-Whitney U test. Categorical variables will be compared using  $\chi^2$  or Fisher's exact tests. Times to achieve full enteral feeding will be compared by the log rank test. Multiple Cox regression analysis will be used to adjust for covariates, such as gestational age and birth weight. IBM SPSS software (current version at the time of publication) will be used for all calculations and a p-value of <0,05 will be considered significant.

Interim analysis will be conducted when 35 infants have been recruited in each study arm (estimated about 1,5 years from study start). Another interim analysis will be conducted when 65 infants have been recruited in each study arm (estimated about 3 years from study start). Unplanned interim analysis will also be conducted in case of subjectively estimated too obvious difference between the groups regarding the primary outcomes, at any time during the study. The study will be discontinued as soon as an interim analysis shows statistically significant results regarding the primary outcomes or severe adverse events.

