## **Secondary outcomes**

Time to regaining of birth weight, growth, BPD, IVH, PDA, ROP, small intestinal perforation, sepsis, hyperbilirubinemia, mortality, adverse events, age at the time of discharge from hospital, number of days on PN, IFALD, and neurological development.

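### Growth at a fixed age is to be compared only by unadjusted tests; a linear model using birth weight and gestational age would be more precise at almost no cost

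*Combined protocol and SAP*

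**What the plan says.** The Statistical analysis section has one rule for numerical outcomes: "Numerical values will be compared between intervention and control groups using t-tests or the Mann-Whitney U test". The choice between the two tests follows a normality check: "We will use the Anderson-Darling test to assess the normality of the data". Neither test takes covariates.

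The same section plans one adjusted analysis: "Multiple Cox regression analysis will be used to adjust for covariates, such as gestational age and birth weight". It comes straight after the log-rank comparison of time to full enteral feeding.

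Growth appears among the secondary outcomes ("Time to regaining of birth weight, growth, BPD, IVH, PDA, ROP, small intestinal perforation, sepsis"), with no metric or time point. The Follow-up section says what is gathered to full-term corrected age, "growth parameters (weight, length, head circumference) and mortality will be collected by the investigators", and adds that "data on children’s growth and neurological development will be collected from the electronic medical records, until the age of 5,5 years".

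Of the values at birth, gestational age defines eligibility. Birth weight is a named Cox covariate and is needed for the outcome on regaining it. Length and head circumference at birth are not named. Findings in the unit are said to be "routinely and continuously registered in detail, with the use of medical computer software, during the whole hospitalization period", so these two were probably recorded, but that is an inference.

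**The concern.** Cox regression models the time to an event. It could serve time to full feeding or time to regain birth weight, but it has no use for a weight, length or head circumference measured at a set age. Those measures therefore fall to the t-test or the Mann-Whitney test. The plan treats gestational age and birth weight as worth adjusting for in one analysis and leaves them out of another where birth weight is the baseline of the outcome itself.

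What is at stake is precision. Any part of later size that could be predicted at birth stays in the error term of the crude test and widens the confidence interval, so a true growth benefit or harm is somewhat easier to miss. The background links poor feeding to growth failure, so readers will look at this outcome. More infants cannot easily be added either, because recruitment is capped at 130 per arm and by calendar time.

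**Working it through.** **No figure to reproduce.** The only sample size calculation in the document concerns NEC. Nothing is stated about power or precision for growth.

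**Inputs from the document.** About 100 infants per arm, 1:1 allocation, significance level 0.05 (taken here as two-sided).

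**Inputs assumed.**
- r, the correlation between the birth values and later size: 0.2, 0.3, 0.5 and 0.6. With two covariates, read r as the multiple correlation.
- A true difference of 0.4 SD.
- Number measured per arm: 100 (all planned infants), or 85 to allow for deaths and loss.

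**Step 1, variance.** With n per arm and outcome SD set to 1, the crude difference in means has variance 2/n. Under a linear model with the baseline as covariate it is (2/n)(1 − r²), apart from a lost degree of freedom.

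| r | Variance cut, r² | SE ratio, √(1 − r²) | Equivalent n per arm, 100/(1 − r²) |
|---|---|---|---|
| 0.2 | 4% | 0.98 | 104 |
| 0.3 | 9% | 0.95 | 110 |
| 0.5 | 25% | 0.87 | 133 |
| 0.6 | 36% | 0.80 | 156 |

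For example, at r = 0.5: 1 − 0.25 = 0.75, √0.75 = 0.87, 100/0.75 = 133.

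**Step 2, power.** Noncentral t with noncentrality 0.4/√((2/n)(1 − r²)). For the crude test at n = 85 this is 0.4/√(2/85) = 0.4/0.153 = 2.61.

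| n per arm | Crude t-test | r = 0.2 | r = 0.3 | r = 0.5 | r = 0.6 |
|---|---|---|---|---|---|
| 100 | 80.4% | 81.9% | 83.9% | 90.1% | 94.0% |
| 85 | 73.7% | 75.4% | 77.6% | 84.9% | 90.0% |

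**Step 3, check by simulation.** With 2,000 simulated trials per setting, 100 per arm and a difference of 0.4 SD, the t-test had 78–80% power and Mann-Whitney 76–78%. The adjusted model had 81% at r = 0.2, 83% at 0.3 and 90% at 0.5, in line with the formula.

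**Step 4, if growth means change from birth.** With equal SDs, a change score has variance 2(1 − r) relative to the crude final value: 1.6 at r = 0.2, 1.4 at 0.3, 1.0 at 0.5 and 0.8 at 0.6. The adjusted model gives 0.96, 0.91, 0.75 and 0.64. A change score is therefore less precise than the adjusted analysis at each assumed r, and less precise than the raw final value when r is below 0.5.

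**The case against.** The strongest reply has four parts.

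- **Growth is undefined.** The document never says that attained size at GA 40+0 is the endpoint. A t-test on weight gain or on change in z-score would also fit the plan and would already use the birth value in part. This stands as a criticism of any single power figure, and the missing definition is a gap in its own right. It does not rescue the crude rule, as Step 4 shows.
- **The benefit is unknown.** No correlation is given. At r = 0.2 to 0.3, which may be what applies at 5.5 years, variance falls by only 4–9% and power rises by about 2 to 4 points. This stands, and it limits the size of the point.
- **Birth values are only partly documented.** It is tempting to assume that all three birth measurements are in hand for every infant. The document supports that for birth weight and gestational age only, so the remedy has to work without birth length and head circumference.
- **Early growth may be covered already.** The Cox sentence is not confined to time to full feeding and could serve time to regain birth weight, the growth-related outcome named in the study hypothesis. That is fair; the gap concerns size at a fixed age.

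A reader might also infer that the crude test is biased because birth size could differ between arms by chance. The document does not support this. Allocation is randomised, the test is valid, and its confidence interval already allows for chance imbalance.

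**Conclusion.** The point holds as a loss of efficiency. The plan offers only unadjusted tests for growth at a fixed age, its single adjusted method does not apply there, and at least two useful baseline values are available. The gain is 4%, 9%, 25% or 36% of variance at r = 0.2, 0.3, 0.5 or 0.6. That runs from hardly noticeable to the equivalent of about 56 more infants per arm on a base of 100. The correlation, the number measured and the 0.4 SD difference are all assumptions; only the planned 100 per arm comes from the document.

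Two stronger readings should be resisted. One is that most of the spread in later size is predictable at birth: the document has no data on this, and even r = 0.6 explains only 36%. The other is that the trial's main findings are weakened: growth is one of many secondary outcomes, the sample size was not set for it, and the analyses of time to full feeding and NEC are unaffected.

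**What to change.** Before the data are examined, add to the Statistical analysis section:

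- Weight at GA 40+0, and at one stated later age, will be analysed by linear regression on arm with birth weight and gestational age at birth as covariates. The adjusted mean difference will be reported with its 95% confidence interval.
- Length and head circumference will be analysed in the same way, with the corresponding birth value and gestational age where birth values are recorded, and otherwise with birth weight and gestational age.
- The t-test or Mann-Whitney comparison will be kept as a sensitivity analysis.

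The growth measures and ages should be named in the Secondary outcomes section so that the model has a defined target.

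The cost is a few sentences. For weight, the covariates are already held and the model runs in the software named in the plan. For the other two measures, someone must check whether the birth values were recorded.

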## Study hypothesis

Regular intestinal lavage in preterm infants of GA between 22+0 and 26+6 weeks facilitates faeces evacuation, shortens the TFF and time to regaining of birth weight, thereby decreasing the risk of sepsis (through shorter intravascular access) and NEC.

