### **Further specifications:**

Sepsis definition: positive blood, urine and/or CSF culture, clinical deterioration and laboratory inflammatory response\*.

A blood culture indicating growth of coagulase-negative staphylococci (CoNS) will be considered as false positive if following criteria are not fulfilled:

1. clinical symptoms
2. two separate blood cultures with the same antibiotic resistance pattern and/or central venous/arterial line prior to onset.
3. laboratory results indicating infection\*

Culture-proven sepsis will be further classified as early (<72 hours postpartum) or late (≥72 hours postpartum) onset and if caused by CoNS or not.

\* Laboratory inflammatory response (one of the following is needed):

1. LPK < 5 or > 20 ( $\times 10^9$  cells/L)
2. TPK < 100 ( $\times 10^9$  cells/L)
3. CRP > 15 mg/L

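### The p<0.05 rule covers 15 unranked secondary outcomes that are nowhere called exploratory; with no true effect on any, at least one would be labelled significant in about 35–55% of trials

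*Combined protocol and SAP*

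**What the plan says.** Secondary outcomes gives one unranked list. Eleven items come first: "Time to regaining of birth weight, growth, BPD, IVH, PDA, ROP, small intestinal perforation, sepsis, hyperbilirubinemia, mortality, adverse events". Four follow: "age at the time of discharge from hospital, number of days on PN, IFALD, and neurological development". That makes 15.

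Statistical analysis describes the comparisons by type of variable, not by rank of outcome. For numerical data, "Numerical values will be compared between intervention and control groups using t-tests or the Mann-Whitney U test". Categorical data get the chi-square or Fisher's exact test. The paragraph on methods ends with a sentence that names the software for all calculations and adds that "a p-value of <0,05 will be considered significant". The threshold carries no restriction to the primary outcomes.

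The protocol contains no adjustment for multiple testing, no order of testing, no key secondary outcome, and no statement that secondary results are exploratory or descriptive.

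Study hypothesis does single out two of the 15. It expects lavage to shorten the time to regaining birth weight, "thereby decreasing the risk of sepsis (through shorter intravascular access) and NEC". Secondary outcomes gives neither sepsis nor birth-weight regain any priority.

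**The concern.** Fifteen outcomes tested at 5% each give many chances for a false positive, and the plan's one rule puts the same label on all of them. A chance p=0.04 for PDA would be called significant in the same sense as a result for sepsis, which the study hypothesis names. A reader of the final report could not tell from the plan which secondary results were meant to bear weight.

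At stake is how the secondary results may be read. The data, the sample size and the analyses of TFF and NEC are unaffected. The two primary outcomes and the interim analyses raise their own multiplicity questions, which are separate from this point.

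**Working it through.** The plan states no error rate for the secondary outcomes, so there is no figure of its own to reproduce.

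**Inputs from the protocol**
- Secondary outcomes: 11 + 4 = 15.
- Threshold: 0.05 per test (Statistical analysis). Whether tests are one- or two-sided is not stated; two-sided is assumed.
- Infants per arm: about 100 (Sample size calculation and estimated duration of the study).
- IVH about 20% and PDA about 60%; almost all infants have some degree of BPD and ROP (Background).

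**Inputs assumed:** the correlations between outcomes, and all other event rates.

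**Independent tests, no true effect on any outcome**

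P(at least one p<0.05) = 1 − 0.95^k; expected number of false positives = 0.05 × k.

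| Family | k | P(at least one) | Expected |
|---|---|---|---|
| All named secondary outcomes | 15 | 53.7% | 0.75 |
| Without mortality, perforation and adverse events | 12 | 46.0% | 0.60 |
| Without BPD and ROP | 13 | 48.7% | 0.65 |
| Growth counted as three measures | 17 | 58.2% | 0.85 |

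**Correlated tests**

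With equally correlated normal test statistics, each two-sided at 5%:

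| Correlation | 15 outcomes | 12 outcomes |
|---|---|---|
| 0 | 53.7% | 46.0% |
| 0.2 | 50% | 43% |
| 0.4 | 41% | 36% |
| 0.5 | 36% | 32% |

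A correlation of 0.7 across all 15 would give 26%. So strong a correlation over outcomes as different as ROP, IFALD and age at discharge seems unlikely, but the documents cannot rule it out.

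**Effect of the choice of test**

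A simulation used ten yes/no and five numerical outcomes with 100 infants per arm. Assumed rates were BPD and ROP 95%, PDA 60%, hyperbilirubinemia 50%, sepsis 30%, IVH and mortality 20%, adverse events and IFALD 10%, and perforation 5%. Correlations between the underlying patient-level variables ran from 0 to 0.5, with 4,000 trials per setting. At least one p<0.05 occurred in 46–55% of trials with the chi-square test and 36–44% with Fisher's test throughout, because Fisher's test is conservative.

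**What moves the figure**
- Down: stronger correlation, Fisher's test throughout, or BPD and ROP analysed as yes/no. Nearly every infant has both, so such a test would rarely reach p<0.05.
- Up: splitting outcomes. Follow-up records growth as weight, length and head circumference. Further specifications says "Culture-proven sepsis will be further classified as early" or late onset, and by whether CoNS caused it. Adverse events cover several distinct possibilities. Growth and neurological data run to 5.5 years with no single time point named.

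About 35–55% is therefore a fair range for exactly 15 tests.

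**The case against.** The strongest reply is that secondary outcomes are by convention supportive, and that the protocol already respects this. It separates primary from secondary outcomes under their own headings, sizes the trial on NEC, and ties efficacy stopping to the primary outcomes. A reader who sees all 15 results can discount an isolated p<0.05.

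Much of this stands. A reader might infer that a trial of a useless lavage would declare a benefit or harm about half the time, or that the plan treats secondary results as confirmatory. The documents support neither. The rule says only what will be considered significant; nowhere does the protocol say that a secondary result would support a conclusion that lavage works. About half is also the upper part of the range, and it depends on independence or weak correlation.

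Two things remain. The separation of primary from secondary outcomes is not carried into Statistical analysis, where one unrestricted threshold applies, and the convention is not written down. Nor are all secondary items free of consequence: the same sentence that stops the trial for significant primary results also names severe adverse events.

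A further fair objection is that the 15-outcome figure includes mortality, perforation and adverse events, which nobody would want to adjust. The 12-outcome figure meets this and is still about 32–46%.

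**Conclusion.** The point holds as a labelling defect. The plan's only rule calls any p<0.05 significant, 15 unranked secondary outcomes fall under it, and nothing marks them as exploratory. With no true effect on any of them, the chance of at least one such label is about 35–55%, or about 32–46% without the three safety outcomes. At the low end of the first range that is seven times the nominal 5% (35/5).

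These figures rest on two-sided tests, one test per named outcome, and correlations between 0 and 0.5 that the documents do not give. The point does not undermine the primary analyses. It is worth correcting because the correction is cheap and settles before the data are seen what the secondary results can be used to claim.

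**What to change.** In Statistical analysis:

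1. Restrict the p<0.05 significance rule to the primary outcomes.
2. State that all secondary outcomes are exploratory and will be reported as effect estimates with unadjusted 95% confidence intervals and no significance claim. State that mortality, perforation and adverse events are likewise reported unadjusted, so that signs of harm are not suppressed. Word this so that the existing provision on severe adverse events at interim analyses is not altered by accident.

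Optional: if the sponsor wants a formal claim on the two hypothesised secondary outcomes, name sepsis and time to regaining birth weight as key secondaries. Test them by Holm's method at 5% (the smaller p-value against 0.025 and, if that succeeds, the other against 0.05), only after success on the primary outcomes. The plan must then define success on its two primaries, and the significance rule must be worded to include the key secondaries. This is a design preference; the two changes above already answer the point.

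The cost is two sentences, with no change to sample size, data collection or care. The downside is that an isolated p<0.05 on a secondary outcome outside any named key secondaries can no longer be claimed as a significant effect.
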